8.6 Analysis of Immune Response

Approximately 23 mL of blood will be collected on Day 1 (prior to administration of HS130/HS110) and Day 8 of Cycle 1 and Cycle 2, and at 30-day safety follow-up visit for the following immune response assessments.

8.6.1 Analysis of Immunological Effect

Immune-phenotyping of patient's peripheral blood sample will be performed by flow cytometry, which may include but is not limited to surface and intracellular markers that define naïve T cells (CD4 and CD8), central memory T cells (CD4 and CD8), effector T cells (CD4 and CD8), memory T cells (CD4 and CD8), senescent T cells (cytotoxic and helper), terminal differentiated senescent T cells (cytotoxic and helper), natural killer (NK) cells, natural killer T cells (NKT), T regulatory cells, proliferative T regulatory cells, activated T cells (helper and cytotoxic), proliferative T cells (helper and cytotoxic), T cell markers of exhaustion (helper and cytotoxic; CTLA-4, PD-1, TIGIT, TIM3).

Immune phenotype profiling to determine proportions of NK and T cell subsets for levels of activation, memory and exhaustion will be performed from blood samples collected on Day 1 (prior to administration of HS130/HS110) and Day 8 for Cycle 1 and Cycle 2, and at 30-day safety follow-up visit. The goal of this analysis will be to establish an immunologically active clinical dose for the combination of HS-130 and HS-110.

8.6.2 Immune Reactivation Response

Immune reactivation response to CTA expressed in HS-110 will be evaluated by determining antigen-induced secretion of cytokines IFN γ , granzyme B (gzB) from patients PBMCs via ELISPOT from blood samples collected Day 1 (pre-dose) and Day 8 for Cycle 1 and Cycle 2 and at 30-day safety follow-up visit. Number of cells responding over the course of treatment after subtraction of appropriate patient controls will be calculated.

8.7 Analysis of Pro-inflammatory Cytokines and Chemokines

Approximately 3 mL of blood samples will be collected at the following time-points during Day 1 of Cycle 1 and Cycle 2 for determination of serum cytokines and chemokines using an extensive panel of markers that may include but is not limited to, G-CSF, GM-CSF, IFN-gamma, IFN-alpha, IL-1alpha, IL-1beta, IL-2, IL-3, IL-4, IL-5, IL-6, IL-7, IL-8, IL-9, IL-10, IL-12p40, IL-13, IL-15/15R, IL-17A, IL-18, IL-22, IL-23, IL-27, IL-28, IL-31, IP-10/CXCL10, LIF, MCP-3/CCL7, M-CSF, MIP-1alpha/CCL3, MIP-1beta/CCL4, MIP-2/CXCL2, RANTES/CCL5, TNFalpha, ENA78/CXCL5, and Eotaxin-1/CCL11.

- Day 1: Prior to administration of HS130/HS110
- Day 1: 2hr \pm 10 minutes after completion of HS130/HS110 treatment

For Cycle 3 and beyond cytokine/chemokine testing will only be performed if the patient is symptomatic (i.e. flu-like symptoms, fever, or allergic reactions).

8.8 Bioinformatics Analysis of CTAs and Shared Antigen Expression

Archival tissue from patients will be sent for bioinformatics analysis (e.g. RNA sequencing) of overexpressed CTAs and to study shared antigen expression with HS-110.

8.9 Exploratory Biomarkers

Biopsy samples will be collected from patients during screening/baseline and within 5-14 days after patients have completed second dose of treatment with the HS-130/HS-110 combination drug product. Archival tissue may be substituted for fresh biopsy during screening/baseline, if collected less than 6-

months prior to Cycle 1 Day 1 and the local pathologist confirms that an adequate amount of tissue/tumor cells exist to allow completion of all testing as outlined in the Tumor Biopsy Collection Manual.

Biopsies should only be collected from lesions considered safely accessible, either image-guided or palpable cutaneous or sub-cutaneous lesions. For patients on continuous anticoagulant therapy, study-specific biopsies should not be done unless local guidelines to mitigate the risk of hemorrhage are followed and the procedure can be done with minimal risk for the patient.

Genomic, immunohistochemistry and proteomic analyses of the collected tumor tissue may be performed to identify biomarkers predictive of response or resistance to HS-110/HS-130, for example by multiplex immunohistochemistry (mIHC). Immunohistochemistry analysis using multiplexed immune markers on the collected on-treatment biopsy and could be compared to baseline biopsy to study effect of HS-110/HS-130 combination treatment on patient tumors and could be correlated with clinical response. This exploratory analysis could change in line with scientific understanding and technical development as the clinical study progresses. Please note that pre-treatment and/or post-treatment tissue samples will only be collected if it poses limited risk to the patient.

9.0 STATISTICS

Demographic data and disease-related characteristics will be summarized using descriptive statistics (count and percent, mean, median, standard deviation, minimum, maximum). Continuous variables will be presented by n, mean, median, standard deviation and range (min and max) as appropriate. Data will be presented by each dose cohort. All patient data, efficacy and safety data will be summarized.

9.1 Analysis Populations

Safety Evaluable Population: All patients who received at least 1 dose of the study treatment.

Efficacy Evaluable Population: All patients with pre-treatment measurable disease by RECIST 1.1¹, who had at least one radiological assessment after pre-treatment or discontinued study treatment early due to disease progression.

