5.4.2 Replacement of Subjects

Patients who discontinue due to toxicity (related to study drug) during the 4-week DLT window of observation of Cycle 1 and Cycle 2, or who do not receive all doses due to toxicity in Cycle 1 and Cycle 2, will not be replaced. Patients who discontinue or who do not receive at least two combination doses of HS-130/HS-110 for any reason other than toxicity during Cycle 1 and 2 will be replaced. Note, that all patients who enrolled in the study will be included in assessment of DLT per Section 6.1.2.

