The first cohort will employ an accelerated design to evaluate the first 4 dose levels in single patients. There will be a staggered enrollment with a minimum 1-week delay between each patient in cohort 1. If any drug-related \geq Grade 2 (other than Grade 2 injection site reaction with pain) event occurs during the first cycle of treatment, the study will revert to 3+3 design starting at that dose level.

Subsequent cohorts in the dose escalation phase will enroll patients following the standard 3+3 design. Three patients will be enrolled in each subsequent dose cohort and enrolled with a (minimum) 1-week staggered delay (i.e. Patient 2 to be dosed \geq 1-week after Patient 1 received the first dose, and Patient 3 to be dosed \geq 1-week after Patient 2 received the first dose).

In the 3-patient cohorts (i.e. 3 patients treated at the same dose), if 1 out of 3 patients experience a DLT during the first two treatment cycles, the dose cohort will be expanded up to 6 patients. If \geq 2 out of 6 patients experience DLTs, the MTD has been exceeded, and dose escalation will cease. Up to 3 additional patients will be enrolled at the next lowest dose if only 3 patients were treated at that dose level, to confirm safety of that dose. If a DLT is observed already with the first patient in Cohort 1, the Safety Review

Committee (Section 8.1.2.8.1) may suggest and approve a dose de-escalation cohort with at least 50 % reduction of HS-110 and HS-130 (dose level -1).

Once all patients in a cohort have completed the first two cycles of dosing and received at least 2 doses of HS-130/HS-110, the safety and tolerability of the combination treatment administered will be reviewed by the safety review committee (SRC). If 0 out of 3 patients or 1 out of 6 patients experience a DLT, then the SRC may recommend enrollment at the next higher dose level.

Any patient who does not receive two doses of the study treatment during the DLT window of observation (first 2 cycles/4 weeks), for reasons other than study drug-related toxicity and did not experience a DLT will not be taken into account in the assessment of the overall DLT rate for the particular dose level cohort and will be replaced.

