- i: Approximately 23 mL blood per draw Day 1 (pre-dose) and Day 8 for C1 and C2, and at 30-day safety follow-up visit for immune response labs (See Section 8.6).
- j: Cytokines and chemokines sample collection on Day 1 for C1 and C2 at time-points: Before HS130/HS110 treatment, and 2 hr ± 10 minutes after treatment. For C3 and beyond only if the patient is symptomatic i.e. flu-like symptoms, fever, or allergic reactions. (Approximately 3 mL blood per draw).
- k: Pre-treatment biopsy (archival tissue may be submitted if collected less than 6-months prior to C1D1 and the local pathologist confirms that an adequate amount of tissue/tumor cells exist to allow completion of all testing as outlined in the Specimen Collection Manual) and on-treatment biopsy collected within 5-14 days after patient completes 2nd dose of HS-130/HS-110 for genomic and proteomic analysis of exploratory biomarkers (e.g. mIHC). Biopsy should be collected for patients with accessible tumor lesions, incl. metastases (e.g. lymph node metastases) where it is considered feasible without a risk of complications for the patient. Coagulation parameters and blood cells should be assessed and reviewed per institutional standard prior to any biopsy.
- l: HS-130 and HS-110 will be administered via intradermal injections/re-injections (up to 10 total) on Day 1 of each cycle, depending on the assigned dose level. (See section 6.1 Drug preparation and administration)
- m: All assessments should be performed at 30 days ± 3 days after the last treatment, during the 30-day safety follow-up visit.
- n: If a patient stops treatment for any other reason than progressive disease, radiological assessments will continue every 12 weeks starting from the date of patient's last dose until disease progression or initiation of new anti-cancer treatment.
- o: Survival status and subsequent anti-cancer therapy information will be collected approximately every 12 weeks in a clinic visit, or by telephone from the time of disease progression or initiation of new anti-cancer treatment until death.
- p: Each cycle is 14 days.

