7.5 Post-treatment Follow-up (\pm 1 week)

The following assessments will be performed every 12-weeks starting from the date of last dose for any patient that stops treatment for any reason other than progressive disease until disease progression or if the patient starts a new treatment. Any AEs deemed related to study drug will also be recorded.

- Record concomitant medications and/or treatments
- Record Adverse events
- Imaging for tumor measurements (CT scan or MRI)

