8.2 Efficacy Assessments

Patient's disease status will be monitored by clinical and radiological assessment (CT scans or MRI) as per RECIST 1.1¹ criteria (Section 8.2.1). Patient response per RECIST 1.1¹ will be evaluated as complete response, partial response, stable disease, or progressive disease.

For the purpose of this study, patients will be evaluated after every 8-weeks \pm 1-week from C1D1. In the event objective response (PR or CR) is noted, changes in tumor measurements must be confirmed by repeat assessments that should be performed at least 4 weeks after the criteria for response are first met. For stable disease (SD), follow-up measurements must meet the SD criteria at least 6 weeks after study entry.

Response to immune therapies may occur after conventional determination of disease progression based on RECIST 1.1¹; therefore, at the Investigator's discretion patients may continue to receive the HS-130/HS-110 combination treatment after progressive disease is first observed.

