8.2.1.2 Measurable Disease

Measurable disease is defined by the presence of at least one measurable lesion. Measurable lesions are defined as those that can be accurately measured in at least one dimension [longest diameter (LD) in the plane of measurement to be recorded] with a minimum size of:

- 10 mm by CT scan (CT scan slice thickness no greater than 5 mm)
- 10 mm caliper measurement by clinical exam (lesions which cannot be accurately measured with calipers should be recorded as non-measurable)
- 20 mm by chest x-ray

Malignant lymph nodes: To be considered pathologically enlarged and measurable, a lymph node must be ≥ 15 mm in short axis when assessed by CT scan (CT scan slice thickness no greater than 5 mm).

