8.2.1.10 Confirmatory Measurement/Duration of Response

8.2.1.10.1 Confirmation

To be assigned a status of PR or CR, changes in tumor measurements must be confirmed by repeat assessments that should be performed at least 4 weeks after the criteria for response are first met. In the case of SD, follow-up measurements must have met the SD criteria at least once after study entry at a minimum interval of 6-weeks.

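### The only efficacy set leaves out treated measurable-disease patients who were never re-scanned and did not stop for progression; barring caliper-only responses, a response proportion on it equals or exceeds the all-treated figure

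*Combined protocol and SAP*

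**What the plan says.** Section 9.1, repeated in the synopsis, defines two populations. The Safety Evaluable Population needs one dose. The Efficacy Evaluable Population needs measurable disease before treatment, and it is limited to patients "who had at least one radiological assessment after pre-treatment or discontinued study treatment early due to disease progression". Measurable disease is not an inclusion criterion in Section 5.1.

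Section 9.3 assigns the safety data to the safety set. Section 9.4 assigns no set to BOR, overall survival (OS) or progression-free survival (PFS); it says only that these are determined patient by patient.

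On what counts as a response, Section 8.2.1.10.1 says: "To be assigned a status of PR or CR, changes in tumor measurements must be confirmed by repeat assessments". Section 8.2 has the first post-baseline evaluation at 8 weeks ± 1 week from Cycle 1 Day 1.

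Section 5.4 lists adverse events, withdrawal by the subject, loss to follow-up, non-compliance, physician decision and death separately from progressive disease. Imaging after such a stop is planned. Table 3, note n begins: "If a patient stops treatment for any other reason than progressive disease, radiological assessments will continue every 12 weeks starting from the date of" the last dose. Section 7.5 runs this follow-up "until disease progression or if the patient starts a new treatment".

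Section 5.4.2 says that patients who stop, or do not receive two combination doses, "for any reason other than toxicity during Cycle 1 and 2 will be replaced".

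**The concern.** Membership of the efficacy set depends on events after dosing. A patient with measurable disease may be dosed and then die without recorded progression, withdraw, be lost or start other therapy before any new scan. That patient drops out of the denominator and could not have been in the numerator. Unless this is offset, the omission works in one direction.

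The plan has no rule that counts such patients as non-responders, and no second response analysis in all treated patients. The short list of BOR categories in Sections 8.3, 9.2.2 and 9.4 (CR, PR, SD) also gives them no place. Section 8.2 says that response "will be evaluated as complete response, partial response, stable disease, or progressive disease", and Table 6 also assigns PD and NE as best responses.

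What is at stake is how the response data read. Section 9.6 allows response at a dose level or in a tumour type to prompt an amendment for cohort expansion, and Section 9.0 presents data by dose cohort, where denominators are very small.

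**Working it through.** The plan states no response rate, dropout rate or calculated sample size, so there is no figure to reproduce. The check has three parts.

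**1. Who is excluded.** Among treated patients with measurable disease at baseline:

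| Course after first dose | In the efficacy set? |
|---|---|
| At least one post-baseline scan | Yes |
| No scan, stopped early for progression | Yes |
| No scan, stopped for any other Section 5.4 reason | No |

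The third row can occur. The first scan falls at weeks 7 to 9. After a non-progression stop, imaging is due every 12 weeks from the last dose, and it ends if new treatment starts.

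**2. Direction.** Let n be the treated patients with measurable disease, k those in the third row, and r the responders.

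- Proportion in all treated patients with measurable disease: r/n.
- Proportion in the efficacy set, if no excluded patient responded: r/(n − k).
- Difference: r/(n − k) − r/n = rk / [n(n − k)], which is never negative and is zero only if r = 0 or k = 0.

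An enumeration over n = 1 to 30, with k < n and r ≤ n − k, agrees: of 5,425 combinations none fell, 4,495 rose and 930 were equal.

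The premise that no excluded patient responded follows from the confirmation rule, with one gap. Section 8.2.1.2 accepts lesions of at least "10 mm caliper measurement by clinical exam" as measurable, whereas Section 9.1 asks for a radiological assessment. A responder followed only by calipers would be dropped, and the proportion would fall: with n = 3, r = 1 and that responder excluded, 1/3 becomes 0/2. Section 8.2 specifies CT or MRI and Table 3 schedules tumour measurement every 8 weeks, so this case would normally need missed imaging.

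**3. Size by dose cohort.** The values r = 1 and k = 1 are assumptions. I also assume that every treated patient has measurable disease and that any replacement is scanned.

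| Planned cohort | Excluded patient replaced? | All treated | Efficacy set |
|---|---|---|---|
| 3 | No | 1/3 = 33.3% | 1/2 = 50.0% |
| 3 | Yes (4 treated) | 1/4 = 25.0% | 1/3 = 33.3% |
| 6 | No | 1/6 = 16.7% | 1/5 = 20.0% |
| 6 | Yes (7 treated) | 1/7 = 14.3% | 1/6 = 16.7% |

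Replacement applies to non-toxicity losses in Cycles 1 and 2 (weeks 1 to 4). It does not apply to a toxicity stop, or to a loss after week 4 and before the first scan. A replaced patient was still treated. Section 6.1.1 removes such a patient from the DLT rate but says nothing about response.

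These proportions carry almost no precision: the exact 95% intervals are about 1% to 91% for 1/3 and about 1% to 99% for 1/2. Dose levels 1 to 4 start with one patient each, where a percentage means little.

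**The case against.** The strongest reply is that the plan never specifies the estimate in question. No objective response rate is defined. The synopsis gives percentages only where meaningful, and Section 9.4 can be read as covering every patient. On that reading the set does no harm, and the defect is an unnamed denominator. This stands as a limit: the link between BOR and the efficacy set is an inference. But if Section 9.4 means all patients, the Efficacy Evaluable Population has no stated use, so either reading needs a sentence.

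Second, much is already covered. Early progressors are kept, early stoppers are due further imaging, and some losses are replaced. This also stands, and it suggests that k is small. It does not bring k to zero.

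Third, no decision rests on the proportion. Escalation rests on DLTs (Section 6.1.1). The recommended phase 2 dose rests on the MTD, the maximum feasible dose or immunological activity (Section 6.1.3). Expansion would need an amendment, and no response threshold is set. This is why the point is minor.

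Fourth, limiting response to measurable disease is a defensible choice that Section 9.1 states openly. I agree, and the comparison here stays within measurable disease.

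**Conclusion.** The point holds as a minor one. If BOR is summarised on the Efficacy Evaluable Population, the response proportion is equal to or higher than in all treated patients with measurable disease. This rests on two conditions: that Section 9.4 intends that set, and that no response is documented by calipers alone without a post-baseline scan. The size is unknown because the documents do not give the number excluded. With one exclusion and one responder assumed, a three-patient cohort moves by 16.7 percentage points without replacement (50.0 − 33.3) or 8.3 points with it (33.3 − 25.0), far inside the uncertainty of such counts.

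Three stronger readings are tempting and are not supported:

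- A reader might infer that the reported response will certainly be inflated. The set is assigned only by implication, and there may be no such patients.
- A reader might infer that the direction also holds against all treated patients. It does not. Patients with non-target disease only are outside the set as well, and Table 5 allows them a CR, so leaving them out can move the proportion either way.
- A reader might infer bias in OS or PFS. Sections 8.4 and 8.5 measure both from first treatment and count death from any cause, and Section 9.4 does not restrict them to the efficacy set.

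**What to change.** In Sections 9.1 and 9.4:

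- Summarise BOR by dose cohort in all treated patients with baseline measurable disease, using CR, PR, SD, PD and NE as in Table 6. Count patients without any post-baseline tumour assessment as NE, that is, as non-responders.
- List patients with non-target disease only separately, with the Table 5 categories (CR, Non-CR/non-PD, PD, NE).
- Keep the Efficacy Evaluable Population as supportive, and report how many treated patients it excludes and why.
- State that OS and PFS use all treated patients, in line with Sections 8.4 and 8.5.

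Align the category list in Sections 8.3, 9.2.2 and 9.4, and the matching synopsis text, with Section 8.2 and Table 6.

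The cost is wording only: no new data, visits or patients. The downside is that the response proportion may look slightly less favourable.

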9.2 Endpoints

9.2.1 Primary

- Safety and Tolerability: number of patients with TEAEs, SAEs, DLTs.

9.2.2 Secondary

- Best overall response (CR, PR, SD), overall survival, PFS per RECIST 1.1¹.

9.2.3 Exploratory

- Immunological effect assessed by evaluating proportions of natural killer (NK) and T cell subsets for levels of activation, memory and exhaustion using flow cytometry.
- Bioinformatics analysis of overexpressed CTAs and shared antigen expression with HS-110.
- Immune reactivation response to HS-110 CTA -induced secretion of cytokines (e.g. by ELISPOT).

- Changes in pro-inflammatory serum cytokines and chemokines, as well as non-specific inflammatory markers (e.g. C-reactive protein).
- Genomic, immunohistochemical and proteomic analysis of pre-treatment and on-treatment biopsy (collected from patients within 5-14 days after 2nd dose of HS-130/HS-110) for exploratory biomarker analysis.
- Immunologically active dose based on flow cytometry analysis of blood, using immune marker panels of activation and suppression as defined in Section 8.6.1.

9.3 Safety

Safety will be assessed by means of physical examination, weight, vital signs, performance status, laboratory evaluations (hematology, biochemistry, cytokines and chemokines), electrocardiogram (ECG), and recording of concurrent illness/therapy and treatment-emergent adverse events. CTCAE version 5 will be used to grade all toxicities. Patients will also be monitored for any clinical symptoms associated with elevated cytokines levels. All related adverse events will be monitored until resolution. Patients will be monitored for safety and concomitant medications throughout the study.

Safety data will be summarized for the safety evaluable population. These data will include AEs and laboratory parameters. Adverse event terms will be coded using the most current version of Medical Dictionary for Drug Regulatory Activities (MedDRA®).

